3.9.2 Exclusion Criteria

1. Target Disease Exceptions
 - a) Subjects with known or suspected central nervous system (CNS) metastases, untreated CNS metastases, or with the CNS as the only site of disease are excluded. However, subjects with controlled brain metastases will be allowed to enroll. Controlled brain metastases are defined as no radiographic progression for at least 4 weeks following radiation and/or surgical treatment (or 4 weeks of observation if no intervention is clinically indicated), and off of steroids for at least 2 weeks, and no new or progressive neurological signs and symptoms.
 - b) Subjects with carcinomatous meningitis
2. Medical History and Concurrent Diseases
 - a) Subjects with a prior malignancy are excluded (except non-melanoma skin cancers, and in situ cancers such as the following: bladder, colon, cervical/dysplasia, melanoma, or breast). Subjects with other second malignancies diagnosed more than 2 years ago who have received therapy with curative intent with no evidence of disease during the interval who are considered by the Investigator to present a low risk for recurrence will be eligible.
 - b) Other active malignancy requiring concurrent intervention
 - c) Prior organ allograft
 - d) Any anti-cancer therapy (e.g., chemotherapy, biologics, vaccines, or hormonal treatment) including investigational drugs within 4 weeks prior to the first dose of study drug administration, with the exception of GnRH agonist therapy for subjects with prostate cancer and anti-cancer therapies with T-HALF < 4 weeks (e.g. prior use of EGFR TKI (completed at least two weeks prior to first dose of study drug is acceptable).
 - e) Prior therapy with T-cell stimulatory anti-GITR antibody
 - f) Subjects with active, known or suspected autoimmune disease. Subjects with vitiligo, type I diabetes mellitus, residual hypothyroidism due to autoimmune condition only requiring hormone replacement, euthyroid patients with a history of Grave's disease (subjects with suspected autoimmune thyroid disorders must be negative for thyroglobulin and thyroid peroxidase antibodies and thyroid stimulating immunoglobulin prior to first dose of study drug), psoriasis not requiring systemic treatment, or conditions not expected to recur in the absence of an external trigger are permitted to enroll.

- g) Subjects with interstitial lung disease that is symptomatic or may interfere with the detection or management of suspected drug-related pulmonary toxicity, including subjects with pneumonitis
- h) Chronic Obstructive Pulmonary Disease requiring recurrent steroids bursts or chronic steroids at doses greater than 10 mg/day of prednisone or the equivalent
- i) Subjects with a condition requiring systemic treatment with either corticosteroids (> 10 mg daily prednisone equivalents) or other immunosuppressive medications within 14 days of study drug administration except for adrenal replacement steroid doses >10 mg daily prednisone equivalent in the absence of active autoimmune disease. **Note:** Treatment with a short course of steroids (< 5 days) up to 7 days prior to initiating study drug is permitted.
- j) Uncontrolled or significant cardiovascular disease including, but not limited to any of the following:
 - i) myocardial infarction or stroke/transient ischemic attack within the past 6 months
 - ii) uncontrolled angina within the past 3 months
 - iii) any history of clinically significant arrhythmias (such as ventricular tachycardia, ventricular fibrillation or torsades de pointes)
 - iv) QTcF prolongation > 480 msec
 - v) history of other clinically significant heart disease (e.g., cardiomyopathy, congestive heart failure with New York Heart Association functional classification III-IV, pericarditis, significant pericardial effusion)
 - vi) requirement for daily supplemental oxygen therapy
 - vii) Subjects with history of myocarditis, regardless of etiology
- k) History of any chronic hepatitis as evidenced by:
 - i) Positive test for HBsAg
 - ii) Positive test for qualitative hepatitis C viral load (by PCR)

Note: a.) *Subjects with positive hepatitis C antibody and negative quantitative hepatitis C by PCR are eligible. History of resolved hepatitis A virus infection is not an exclusion criterion*

b.) *Criteria k) do not apply to subjects with hepatocellular cancer, (see section 3.9.1)*
- l) Evidence of active infection ≤ 7 days prior to initiation of study drug therapy (does not apply to viral infections that are presumed to be associated with the underlying tumor type required for study entry).
- m) Known history of testing positive for HIV or known acquired immunodeficiency syndrome. Note: Testing for HIV must be performed at sites where mandated by local requirements
- n) Evidence or history of active or latent tuberculosis infection including purified protein derivative recently converted to positive; chest x-ray with evidence of infectious infiltrate; recent unexplained changes in fever/chill patterns.

- o) Any major surgery within 4 weeks of study drug administration. Subjects must have recovered from the effects of major surgery or significant traumatic injury at least 14 days before the first dose of study drug
 - p) All toxicities attributed to prior anti-cancer therapy other than alopecia and fatigue must have resolved to Grade 1 (NCI CTCAE version 4.03) or baseline before administration of study drug. Subjects with toxicities attributed to prior anti-cancer therapy which are not expected to resolve and result in long lasting sequelae, such as neuropathy after platinum based therapy, are permitted to enroll.
 - q) Use of non-oncology vaccines containing live virus for prevention of infectious diseases within 12 weeks prior to study drug. The use of inactivated seasonal influenza vaccines e.g. Fluzone® will be permitted on study without restriction.
 - r) Use of pRBC or platelet transfusion within 2 weeks prior to the first dose of study drug.
 - s) A known or underlying medical condition that, in the opinion of the Investigator or Sponsor, could make the administration of study drug hazardous to the subjects, or could adversely affect the ability of the subject to comply with or tolerate the study.
3. Physical and Laboratory Test Findings
- a) Positive tests for hepatitis B virus surface antigen, hepatitis B core antibody, or hepatitis C RNA (Subjects with positive hepatitis C antibody and negative quantitative hepatitis C by PCR are eligible.) Additional testing or substitute testing per institutional guidelines to rule out infection is permitted
4. Allergies and Adverse Drug Reaction
- a) History of allergy to nivolumab
 - b) History of any significant drug allergy (such as anaphylaxis or hepatotoxicity) to prior anti-cancer immune modulating therapies (e.g. checkpoint inhibitors, T cell co-stimulatory antibodies)
5. Other Exclusion Criteria
- a) Prisoners or subjects who are involuntarily incarcerated
 - b) Subjects who are compulsorily detained for treatment of either a psychiatric or physical (e.g., infectious disease) illness
 - c) Inability to comply with restrictions and prohibited activities/treatments as listed in [Section 3.10.1](#)

Eligibility criteria for this study have been carefully considered to ensure the safety of the study subjects and that the results of the study can be used. It is imperative that subjects fully meet all eligibility criteria.

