3.9 Study Population

For entry into the study, the following criteria MUST be met prior to dosing on Day 1. No exceptions will be granted.

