 - 3) Prior therapy requirement: Subjects must have received and then progressed or have been intolerant or refractory to at least 1 standard systemic therapy (eg, platinum-based chemotherapy) for metastatic and/or unresectable disease. Subjects who are sensitive to platinum must have received at least 2 prior platinum-containing lines of treatment.
- vi. Hepatocellular Carcinoma - Cohort 8**
- 1) Subjects must have progressive disease, or been intolerant to, at least one line of therapy or refuse treatment with sorafenib.
 - 2) Child-Pugh score of 6 points or less and must not have encephalopathy and total bilirubin $\leq 1.5 \times$ upper limit of normal (ULN; ie, Child Pugh A)
 - 3) Subjects must have testing for hepatitis B surface antigen (HBsAg), hepatitis B surface antibody, hepatitis B core antibody, hepatitis B DNA polymerase chain reaction (PCR), hepatitis C antibody, or hepatitis C RNA PCR.
 - 4) Subjects with hepatitis B infection must have hepatitis B DNA viral load < 100 IU/mL and must be on anti-viral therapy per institutional guidelines.
 - 5) Subjects with hepatitis B infection must not have co-infection with hepatitis C or hepatitis D (must obtain hepatitis D antibody testing).
 - 6) Subjects must not have clinically significant ascites or clinically significant variceal bleeding.
- vii. Solid tumors types as listed in part D are a part of Cohort 10, Part E**
- 1) Subjects with NSCLC (prior I/O therapy), bladder, SCCHN, ovarian cancer and hepatocellular cancer. Must meet inclusion criteria listed in part D. Must not meet exclusion criteria
 - 2) Must have received, and then progressed or been intolerant to, at least one standard treatment regimen in the advanced or metastatic setting, if such a therapy exists must meet inclusion criteria as stated above. Subjects who refuse or are

ineligible for standard therapy will be allowed to enroll provided their refusal/ineligibility is documented in medical records

h) Conditions for all tumor types

- 
- 2) Not applicable for revised protocol 03
 - 3) Subjects must have ≤ 5 prior treatment regimens. The following are not considered separate lines of treatment: addition of a compound to an on-going regimen, re-starting the same regimen after a drug holiday, or switching from IV to oral therapy.

Parts A-E:

Not applicable as of revised protocol 03.

Adequate organ function for subjects with solid tumor histologies, which is defined as follows:

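### Exclusion 3a omits the HCC exemption given for exclusion 2k, so it conflicts with the hepatitis B entry conditions in HCC inclusion vi.4-5

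*Combined protocol and SAP*

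**What the plan says.** Five places in the combined protocol and SAP bear on viral hepatitis in HCC.

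- **Section 3.9.1, vi (HCC, Cohort 8).** Item 3 calls for hepatitis B and C testing. Item 4 begins "Subjects with hepatitis B infection must have hepatitis B DNA viral load < 100 IU/mL" and also requires antiviral therapy. Item 5 rules out hepatitis C or D co-infection in those subjects. Item vii carries the Part D criteria over to the HCC subjects in Cohort 10 and says the exclusions apply there too.
- **Section 3.9.2, exclusion 2k.** This opens "History of any chronic hepatitis as evidenced by" and lists hepatitis B surface antigen and hepatitis C viral load. Note b then says "Criteria k) do not apply to subjects with hepatocellular cancer" and points back to Section 3.9.1.
- **Section 3.9.2, exclusion 3a.** This excludes "Positive tests for hepatitis B virus surface antigen, hepatitis B core antibody, or hepatitis C RNA". It has two softening clauses: "Subjects with positive hepatitis C antibody and negative quantitative hepatitis C by PCR are eligible", and "Additional testing or substitute testing per institutional guidelines to rule out infection is permitted". Neither mentions HCC.
- **Section 1.6.** The risk/benefit text says that subjects with hepatitis B or C who are at risk of an exaggerated antiviral inflammatory response will be excluded. It refers to Section 3.9.2 and does not mention HCC.
- **Section 3.9.** On the criteria as a whole: "No exceptions will be granted". The closing paragraph of Section 3.9.2 likewise requires every criterion to be met.

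**The concern.** Items vi.4-5 have a purpose only if some HCC subjects with hepatitis B may enter. Note b shows that the authors thought an express waiver was needed to let them in. Exclusion 3a then repeats the surface antigen and hepatitis C RNA exclusions, adds core antibody, and carries no waiver. A site following 3a and a site following note b would enrol different patients under the same cohort label.

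The planned analysis would not bring this to light. Section 8.2 bases efficacy and safety on all treated subjects, and the baseline tables in Section 8.4.1 cover gender, race, age, weight and height, but not viral status. Viral status also matters for reading hepatic events, because Section 6.6 lists viral hepatitis among the alternative causes that must be absent before an event counts as potential drug-induced liver injury. If the mix of virus-positive and virus-negative subjects depends on which criterion a site happened to follow, the HCC response rate and the hepatic safety findings describe a population that the protocol does not fix.

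**Working it through.** The point rests on comparing criteria; no published figure of the plan depends on it. The only figures that apply to the HCC cohort are those in Section 8.1.2 for 40 subjects. With a true ORR of 40%, the binomial probabilities are 0.929 for at least 12 responses, 0.871 for at least 13, and 0.071 for 11 or fewer. The one-sided 90% exact lower limits are 0.162 for 10/40 and 0.271 for 15/40. All agree with the stated 93%, 87%, 7%, 16% and 27%, and none changes here.

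**Step 1: run HCC subject profiles through the criteria**, assuming all other criteria are met.

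| HCC subject | Inclusion vi | Exclusion 2k with notes | Exclusion 3a | Result as written |
|---|---|---|---|---|
| Surface antigen positive, on antivirals, DNA below 100 IU/mL, no C or D co-infection | Meets vi.4-5 | Waived by note b | Excluded | Contradiction, explicit |
| Hepatitis C RNA positive, no hepatitis B | Not mentioned | Waived by note b | Excluded | Contradiction, by inference from the waiver |
| Core antibody positive, surface antigen negative | vi.4-5 apply only if this counts as infection | Not triggered by hepatitis B | Excluded on its wording; the further-testing clause may soften this | Unclear |
| Hepatitis C antibody positive, PCR negative | Not mentioned | Eligible (note a) | Eligible | Can enrol |
| Negative on all tests | No positive result is required | Not triggered | Not triggered | Can enrol |

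**Step 2: look for a clause that overrides 3a.**

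- Note b names criterion k and nothing else.
- Exclusion 2l has its own carve-out for viral infections thought to go with the tumor type. It belongs to 2l and does not amend 3a.
- The further-testing clause in 3a is for ruling infection out. It cannot help a subject whom vi.4 describes as infected.
- Sections 3.9 and 3.9.2 leave no discretion.

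**Step 3: check where core antibody is tested.** The screening serology in Table 5.1-1 and the laboratory list in Section 5.3.2 name surface antigen and hepatitis C tests, but not core antibody. Among the testing requirements only vi.3 names it, so that part of 3a falls mainly on HCC subjects.

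**Step 4: size.** Section 1 says only that HCC incidence varies geographically, largely with hepatitis B and C, and gives no share. If *f* is the assumed share of otherwise eligible HCC candidates whom 3a removes, filling 40 places takes 40/(1 − *f*) candidates, rounded up:

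- *f* = 30%: 40/0.70 = 57.1, so 58
- *f* = 50%: 40/0.50 = 80
- *f* = 70%: 40/0.30 = 133.3, so 134
- *f* = 80%: 40/0.20 = 200

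These values of *f* are illustrations, not estimates. *f* is also not raw seropositivity, because vi.4-5 already remove some hepatitis B-infected candidates.

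**The case against.** The best reply is that this is a missing cross-reference whose intent is plain. Note b, the carve-out in 2l and items vi.3-5 all point towards admitting HCC subjects with controlled hepatitis B. Section 1.6 is a qualified summary that defers to Section 3.9.2, so it adds little independent weight. ORR is a secondary endpoint and no hypothesis is formally tested. The synopsis describes Parts C and D in the past tense and Revised Protocol 05 removes response follow-up, so a correction may come late.

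Much of this stands. A drafting slip is the likeliest explanation, and the documents do not say whether HCC enrolment is still open. But likely intent does not tell a site what to do when 3a is explicit and exceptions are refused.

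A reader might also infer more than the text supports:

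- **That 3a bars every subject with evidence of hepatitis B or C.** It does not: hepatitis C antibody with a negative PCR is expressly eligible.
- **That Cohort 8 cannot enrol its target population.** Items vi.1-2 define that population by prior therapy (or refusal of sorafenib) and liver function, not by viral cause. Enrolment becomes impossible only if *f* is 100%.
- **That inclusion vi expressly admits hepatitis C RNA-positive subjects.** It does not; their admission follows only from the 2k waiver.
- **That a countable number of subjects are eligibility deviations.** Shares of 30% to 80% would give 12 to 32 of 40, but no document supports those shares, and the count also assumes that every site ignored 3a.

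**Conclusion.** The conflict is real and lies in the text. Exclusion 3a lacks the HCC exemption given for 2k and, read literally, excludes the hepatitis B-infected HCC subjects for whom vi.4-5 sets conditions. For hepatitis C RNA-positive HCC subjects the conflict is inferred from the waiver. For core antibody, 3a adds a bar that 2k does not contain. It reaches Cohort 8, planned at about 40 subjects, and the HCC subjects in Cohort 10, whose number is not given. Virus-negative and hepatitis C antibody-positive/PCR-negative HCC subjects are unaffected.

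The conclusion rests on reading the criteria as written and needs no assumption about how common viral hepatitis is. The effect on enrolment and case mix cannot be sized from the documents. Which rule should govern is for the sponsor to decide. The plan should be corrected, because following 3a literally defeats other current criteria.

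**What to change.** Reconcile Section 1.6, Section 3.9.1 vi and exclusions 2k and 3a so that one rule on viral hepatitis in HCC appears throughout. Either route is consistent:

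- **If the HCC provisions stand:** extend the HCC note to 3a, saying whether it covers core antibody and hepatitis C RNA, and qualify Section 1.6. This takes about one sentence in each place.
- **If 3a stands:** remove vi.4-5 and note b, and describe Cohort 8 and the HCC subjects in Cohort 10 accordingly. This is a slightly longer edit.

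In the same revision, align the core antibody element with Table 5.1-1 and Section 5.3.2 if it is kept, and make clear whether vi.3 requires every listed test, since its list is joined by an or.

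For subjects already enrolled, state which rule was applied and classify eligibility deviations against it. If virus-positive HCC subjects are admitted or were enrolled, add viral status to the HCC baseline table and describe HCC response and hepatic safety by it. The data should already come from the vi.3 testing, so no new visits are needed and the added cost is a few descriptive tables. If the cohort is and was virus-negative only, that split is unnecessary.

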3.9.3 Women of Childbearing Potential

Women of childbearing potential (WOCBP) is defined as any female who has experienced menarche and who has not undergone surgical sterilization (hysterectomy or bilateral oophorectomy) and is not postmenopausal. Menopause is defined as 12 months of amenorrhea in a woman over age 45 in the absence of other biological or physiological causes. In addition,

females under the age of 55 years must have a documented serum follicle stimulating hormone, (FSH) level > 40 mIU/mL to confirm menopause.

Females treated with HRT are likely to have artificially suppressed FSH levels and may require a washout period in order to obtain a physiologic FSH level. The duration of the washout period is a function of the type of HRT used. The duration of the washout period below are suggested guidelines and the Investigators should use their judgement in checking serum FSH levels. If the serum FSH level is >40 mIU/mL at any time during the washout period, the woman can be considered postmenopausal.

- 1 week minimum for vaginal hormonal products, (rings, creams, gels)
- 4 week minimum for transdermal products
- 8 week minimum for oral products

Other parenteral products may require washout periods as long as 6 months.

3.10 Concomitant Treatments

3.10.1 Prohibited and/or Restricted Treatments

- a) Immunosuppressive agents (except as stated in [Section 3.10.3](#)), unless they are utilized to treat an AE.
- b) Concomitant therapies are allowed but must be recorded on the case report form (CRF).
- c) Subjects with a condition requiring systemic treatment with either corticosteroids (> 10 mg daily prednisone equivalents) or other immunosuppressive medications within 14 days of study drug administration. Inhaled or topical steroids, and adrenal replacement doses > 10 mg daily prednisone equivalents are permitted in the absence of active autoimmune disease.
- d) Herbal remedies which are not approved in writing by the PI

3.10.2 Other Restrictions and Precautions

It is the local imaging facility's responsibility to determine, based on subject attributes (e.g., allergy history, diabetic history and renal status), the appropriate imaging modality and contrast regimen for each subject. Imaging contraindications and contrast risks should be considered in this assessment. Subjects with renal insufficiency should be assessed as to whether or not they should receive contrast and if so, what type and dose of contrast is appropriate. Magnetic resonance imaging (MRI) contrast should not be given to subjects with severe renal insufficiency (e.g., estimated glomerular filtration rate (eGFR) < 30 mL/min/1.73 m²) because of increased risk of nephrogenic systemic fibrosis in this subject population. In these patients, alternative imaging tests, or MRI without gadolinium should be considered. In addition, subjects are excluded from MRI if they have tattoos, metallic implants, pacemakers, etc.

The ultimate decision to perform MRI in an individual subject in this study rests with the site radiologist, the Investigator and the standard set by the local Ethics Committee.

3.10.3 Permitted Therapy

Subjects are permitted the use of topical, ocular, intra-articular, intranasal, and inhalational corticosteroids (with minimal systemic absorption). Systemic treatment with a short course of steroids (< 5 days) up to 7 days prior to initiating study drug is permitted. A brief course of systemic corticosteroids for prophylaxis (e.g., contrast dye allergy) or for treatment of non-autoimmune conditions (e.g., delayed-type hypersensitivity reaction caused by a contact allergen) is permitted.

- Systemic immunosuppressive agents and the use of systemic corticosteroids are permitted in the context of treating AEs. Subjects receiving corticosteroids for treatment of drug-related AEs must be at < 10 mg/day prednisone or equivalent prior to re-initiation of study therapy for ≤7 days. Subjects may continue to receive HRT.
- Subjects are permitted the use of topical, ocular, intra-articular, intranasal, and inhalational corticosteroids (with minimal systemic absorption).

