3.10.4 Palliative Local Therapy

- Palliative and supportive care for disease related symptoms may be offered to all subjects on the trial after the DLT evaluation period. Limited radiation therapy or surgery to control isolated lesions is permitted for subjects who have investigator assessed clinical benefit following consultation with the BMS Medical Monitor.
- Subjects should not receive study treatment during radiation as the potential for overlapping toxicities with radiotherapy and BMS-986156, or combination of BMS-986156 and nivolumab currently is not known. Anecdotal data suggest that radiotherapy administered to subjects while receiving nivolumab therapy is tolerable. However, because concurrent radiotherapy and immunotherapies in cancer have not been formally evaluated, in cases where palliative radiotherapy is required for a tumor lesion, then BMS-986156 alone or BMS-986156 in combination with nivolumab should be withheld for at least 1 week before, during, and 1 week after radiation. Subjects should be closely monitored for any potential toxicity during and after receiving radiotherapy, and AEs related to radiotherapy should resolve to Grade 1 prior to resuming study therapy.
- Subjects who have received palliative local therapy will be documented as having had disease progression for the purpose of efficacy analyses.

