4.3.4 Dose Delays Due to Toxicity

Subjects who experience a DLT must have study drug held. Subjects who are required to permanently discontinue both study drugs are listed in [Section 4.3.6](#). In addition, all Grade 2 hepatic, pulmonary, renal, gastrointestinal, and neurological AEs should be evaluated and managed per the toxicity management algorithms ([Appendix 4](#)). Subjects not meeting guidelines for permanent discontinuation will be permitted to resume therapy based on the criteria specified below in [Section 4.3.5](#). Subjects eligible to resume study therapy will resume study therapy at the treatment visit following their last received study medication dose.

In Parts A and C, if there is a delay in dosing of BMS-986156 of between 1 -12 days, the procedures at the original scheduled visit should be performed as soon as possible. If the delay is more than

12 days, the visit and dose will be considered missed; the procedures at the next scheduled visit should be performed, and subsequent BMS-986156 doses will follow every 2 weeks.

In Parts B, D and E depending on the dosing schedule (See [Table 5.1-2](#)), if there is a delay in dosing of combination dose (same day dose of BMS-986156 and nivolumab) of between 1 -12 days, If the delay is more than 12 days, the visit and dose will be considered missed; the procedures at the next scheduled visit should be performed, and subsequent combination doses will follow after 2 weeks.

Extensions to the period of dose delays may be granted for individual subjects on a case by case basis after specific consultation and agreement between the Investigator and BMS Medical Monitor in settings where benefit/risk may justify continued study therapy (e.g., subject deriving clinical benefit who requires prolonged steroid taper for management of non-DLT drug-related AEs, or experiences delays for management of a non drug related AE).

The end of cycle tumor assessments (i.e., CT/MRI, positron emission tomography, etc) will continue on an every 8 weeks schedule relative to the subject's 1st dose regardless of any treatment delay incurred.

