4.3.5 Criteria to Resume Treatment

Subsequent dosing with study therapy may resume once drug-related non-DLT AEs resolve to Grade 1 or baseline.

Subjects experiencing AEs not meeting criteria for permanent discontinuation as outlined in [Section 4.3.6](#) may resume treatment with study medication under the following criteria:

- Subjects may resume treatment with study drug when the drug-related AE(s) resolve to Grade ≤ 1 or baseline value with the following exceptions:
 - Subjects may resume treatment in the presence of Grade 2 fatigue;
 - Subjects who have not experienced a Grade 3 drug-related skin AE may resume treatment in the presence of Grade 2 skin toxicity;
 - Subjects with Grade 2 uveitis or eye pain or blurred vision not meeting DLT criteria ([Section 4.3.1](#)) must resolve to baseline prior to resuming study therapy;
 - Drug-related pulmonary toxicity, diarrhea, or colitis, must have resolved to baseline before treatment is resumed;
 - Drug-related endocrinopathies adequately controlled with only physiologic hormone replacement may resume treatment.

If the criteria to resume treatment are met, the subject should restart treatment at the next scheduled time point per protocol.

The consideration to re-initiate study therapy under these exceptions will be made on a case by case basis after considering the overall benefit/risk profile and in consultation between the Investigator and the study sponsor. Any AE with clinical risk will be assessed on a case by case basis with the Investigator and the BMS Medical Monitor to determine the risks and benefits of continuing on therapy following resolution versus discontinuing therapy permanently.

If treatment with study medication is delayed > 6 weeks, the subject must be permanently discontinued from study therapy, except as specified in Section 4.3.6.

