4.3.6 Guidelines for Permanent Discontinuation

Subjects will be required to permanently discontinue both study drugs for the following AEs:

- Any drug related AE occurring at any time that meets DLT criteria as outlined in [Section 4.3.1](#) will require permanent discontinuation with the following **exceptions**:
 - a) Grade 3 diarrhea, nausea, vomiting, or abdominal pain that returns to grade 1 or baseline within 3 days with medical intervention;
 - b) Grade 3 pruritus or rash that returns to grade 1 or baseline within 7 days or baseline with medical intervention;
 - c) Grade 4 electrolyte abnormalities that \leq 72 hours in duration;
 - d) Grade 4 neutropenia \leq 5 days in duration;
 - e) Grade 4 increase in amylase or lipase that is not associated with clinical or radiographic evidence of pancreatitis;
 - f) Grade 4 lymphopenia \leq 5 days in duration.
- Any dosing delay lasting > 6 weeks will be cause for permanent discontinuation. Extensions to the period of dose delays may be granted for individual subjects on a case by case basis after specific consultation and agreement between the Investigator and BMS Medical Monitor in settings where benefit/risk may justify continued study therapy (e.g., subject deriving clinical benefit who requires prolonged steroid taper for management of non-DLT irAEs, or experiences delays for management of a non-drug-related AE).
- Accordingly, dosing delays to allow for prolonged steroid tapers to manage drug-related AEs are allowed. Additionally, dosing delays > 6 weeks that occur for non-drug-related reasons may be allowed if approved by the BMS Medical Monitor.
- Prior to re-initiating treatment in a subject with a dosing delay lasting > 6 weeks, the BMS Medical Monitor must be consulted.
- Tumor assessments should continue as per protocol even if dosing is delayed.

All subjects who discontinue IP should comply with protocol specified follow-up procedures as outlined in [Section 3.3](#). The only exception to this requirement is when a subject withdraws consent for all study procedures including post-treatment study follow-up or loses the ability to consent freely (e.g., is imprisoned or involuntarily incarcerated for the treatment of either a psychiatric or physical illness).

If study treatment is discontinued prior to the subject's completion of the study, the reason for the discontinuation must be documented in the subject's medical records and entered on the appropriate CRF page.

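### Section 3.10.3 sets the low-dose steroid period before redosing as a maximum of 7 days, so one day satisfies it; a minimum was probably meant

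*Combined protocol and SAP*

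**What the plan says.** Section 3.10.3 (Permitted Therapy) allows systemic steroids for treating AEs and then sets a condition for restarting study drug. It covers "Subjects receiving corticosteroids for treatment of drug-related AEs", who "must be at < 10 mg/day prednisone or equivalent prior to re-initiation of study therapy for ≤7 days".

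Other sections that bear on restart or on steroid timing:

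- Section 4.3.5 ties restart to AE grade: "Subsequent dosing with study therapy may resume once drug-related non-DLT AEs resolve to Grade 1 or baseline". It lists some exceptions and gives no steroid dose or duration.
- Section 4.3.6 states that "dosing delays to allow for prolonged steroid tapers to manage drug-related AEs are allowed". Section 4.3.4 gives as an example of an extended delay a "subject deriving clinical benefit who requires prolonged steroid taper for management of non-DLT drug-related AEs".
- Section 3.10.4, directly after the sentence at issue, says that study drug "should be withheld for at least 1 week before, during, and 1 week after radiation".
- Section 3.9.1, in the note on earlier checkpoint-related AEs, requires steroid tapers to have ended no less than 14 days before study therapy starts. Section 3.9.2, item 1(a), requires subjects with controlled brain metastases to have been off steroids for 2 weeks or longer.

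**The concern.** The sentence is a mandatory condition for giving an immune-activating drug, or two of them, again after drug-related toxicity. A condition of this kind normally shows that the AE stays resolved once the steroid dose is low. Written as a maximum, it cannot do that: a subject qualifies after a single day at low dose and stops qualifying as the low-dose period lengthens.

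The AE-grade criterion in Section 4.3.5 does not fill the gap, because it does not ask what steroid dose the subject was on when the grade was recorded. Appendix 4 describes corticosteroids as a primary treatment for these AEs, so a grade recorded one day after step-down may still reflect the higher dose. At stake are subject safety and consistent redosing across sites, in a study whose primary objective is safety and tolerability.

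**Working it through.** The plan gives no figure to reproduce here. The check treats the sentence as a logical rule and compares it with its presumed intent.

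**Inputs.** Dose threshold below 10 mg/day and duration ≤7 days (Section 3.10.3). Dosing every 2 weeks in Parts A to D and every 4 weeks in Part E (Section 3.1). Delay allowance of 1 to 12 days (Section 4.3.4). Delay limit of 6 weeks (Sections 4.3.5 and 4.3.6).

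**Step 1: the two rules.** Let d be the number of days below 10 mg/day before restart, with the steroid still being given.

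| d (days) | As printed (d ≤ 7) | Presumed intent (d ≥ 7) |
|---|---|---|
| 1 | met | not met |
| 2 to 6 | met | not met |
| 7 | met | met |
| 8, 14, 28 | not met | met |

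The rules agree only at d = 7. Days 1 to 6 qualify only under the printed rule, and day 8 onwards only under the presumed one.

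**Step 2: what happens after day 7.** The sentence applies only to subjects receiving corticosteroids. Someone who passes day 7 while still tapering fails the printed condition, but leaves its scope once the taper is complete. The effect is a wait until steroids stop.

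**Step 3: does another reading help?** The phrase could be read as a look-back window instead of a running count. The upper cut-off then disappears, but ≤ admits any window from 1 to 7 days, so there is still no minimum.

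**Step 4: does other text supply a minimum?** Section 4.3.5 uses AE grade only. Sections 4.3.4 and 4.3.6 allow time for tapers but do not say how long the dose must be low before restart. The comparable intervals in Sections 3.9.1, 3.9.2 and 3.10.4 are all minimums. That pattern points to a reversed sign.

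**Step 5: cost of reversing it.** The largest added wait against the printed rule is 7 − 1 = 6 days, which lies inside the 1 to 12 day allowance in Section 4.3.4. If that allowance is not used, Section 4.3.5 sends restart to the next scheduled time point, which may be 14 days away, or 28 days in Part E. The delay limit is 6 × 7 = 42 days, extendable for prolonged tapers with the Medical Monitor's agreement.

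**The case against.** The best case on the other side is that the sentence does little harm in practice. The dose threshold itself is clear. Section 4.3.5 requires resolution to Grade 1 or less or baseline, with listed exceptions, and to baseline for pulmonary toxicity, diarrhea and colitis. It also calls for case-by-case assessment of any AE with clinical risk. Section 4.3.6 requires permanent discontinuation for drug-related events meeting DLT criteria, apart from six listed exceptions. The Appendix 4 algorithms, to which sites are sent for AE management, may contain steroid or restart timing; their figures are not shown. All of this stands and narrows the risk. None of it supplies a low-dose minimum in the text that can be read.

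Three stronger readings are tempting and are not supported.

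- A reader might infer that subjects on a longer taper are shut out of retreatment. They are not: they wait until steroids stop. That delay is conservative, so only the one-day side of the rule is a safety matter.
- A reader might infer a flat contradiction with the taper allowances in Sections 4.3.4 and 4.3.6. The clash is partial. The 7-day limit applies only to time below 10 mg/day, so a long taper mostly above that dose, ending with up to 7 low-dose days, satisfies all three sections.
- A reader might set the sentence against Section 3.10.1(c), which restricts "systemic treatment with either corticosteroids (> 10 mg daily prednisone equivalents) or other immunosuppressive medications within 14 days of study drug administration", and conclude that nobody can satisfy both. Item (c) closely tracks entry exclusion 2(i) in Section 3.9.2. Item (a) of the same list refers to Section 3.10.3 and lifts the bar on immunosuppressive agents with the words "unless they are utilized to treat an AE". The documents do not show that (c) governs redosing after AE treatment, so neither a conflict nor a default 14-day wait can be built on it.

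**Conclusion.** The point holds as a wording error in an operative safety rule and should be fixed. As printed, the condition is met after one day below 10 mg/day and is no longer met at day 8 of a continuing low-dose taper. It matches the presumed rule only at day 7.

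Confidence is high about what the printed text says. That a 7-day minimum was intended is an inference from the comparable intervals, and the documents do not state it. The practical risk is limited to subjects who pass the AE-resolution and review criteria and are not permanently discontinued; their number is not given. No sample size, estimate or other statistical figure is affected. The conclusion is also subject to whatever timing the unseen Appendix 4 figures contain.

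**What to change.** In Section 3.10.3, change ≤7 days to at least 7 days, so that subjects still receiving corticosteroids for a drug-related AE must have been below 10 mg/day for at least a week before study therapy restarts. The sponsor should confirm that this was the intent and that it agrees with the Appendix 4 algorithms. This point needs no change to Section 3.10.1.

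The edit is one phrase and adds no procedures or subjects. The downside is later redosing for some: up to 6 days against the printed rule, or until the next scheduled visit at 2 weeks (4 weeks in Part E) where the Section 4.3.4 allowance is not used.
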